	
Primary Efficacy Analysis
 
The primary endpoint will be analyzed by computing the Pearson (product-moment) and Spearman (rank) correlation between the TUV_{joint} for the biopsied joint and 2 measures of macrophage prevalence:
 
• The fraction of CD206-expressing macrophages visible in the microscope field under 4x and 10x power magnification, measured as the area fraction (AF) $AF = \frac{\text{Total Stained Area}}{\text{Total Field Area}} \times 100\%.$ 
• The volume of synovial tissue in the biopsied joint derived from the ultrasound synovitis score (Vol). The final CD206-expressing macrophage count is defined as the product of Vol and AF defined above. 
A 95% confidence interval for the population correlation coefficient measuring the association between TUV and CD206 expression (as measured via IHC) will be computed using the Fisher's Z-transformation method ($Z = \tanh^{-1} r$) and its asymptotic Normal approximation. Statistical summaries of the marginal distributions of TUV_{joint} and CD206 macrophage count will be provided (mean, standard deviation, number of cases, median, and range).
 
Secondary Efficacy Analyses
 
The degree of co-expression of CD68, CD163, and/or CD206 macrophage types will be assessed by calculating the Pearson (product-moment) correlations and Spearman rank correlations among these variables. The marginal distributions will be summarized by calculating the mean, standard deviation, number of cases, median, and range for each variable.
 
The ability of TUV_{joint} to discriminate among lympho-myeloid, diffuse myeloid, and pauci-immune fibroid types will be assessed by fitting a multinomial logistic regression model with RA pathotype as the response variable and TUV_{joint} as the explanatory variable. ROC curves will be generated for the multinomial logistic model using the lympho-myeloid type as the base class. No inferential statistics will be generated for this endpoint.

--	---

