In recent years, synovial biopsy-enabled studies have greatly increased our understanding of the pathological processes occurring within the inflamed joints of RA patients (Orr 2017). An important finding of these studies has been that the inflammatory cell compositions of RA inflamed joints can vary between patients (Townsend 2014, van de Sande 2016). The biopsy specimens obtained from different RA patients can have different numbers and densities of macrophages and monocytes, lymphocytes and lymphocyte containing structures, and fibroblast-like synoviocytes (Orr 2017). These differences in cellular composition suggest that RA inflammation can be divided into 3 pathotypes, referred to as diffuse myeloid, lympho-myeloid, and fibroid, respectively (Dennis 2014, Astorri 2015). High densities of macrophages can occur in both the myeloid and lymphoid pathotypes, whereas the fibroid pathotype is largely devoid of both macrophages and lymphoid cells. These pathotypes are not fully discrete, with some overlap occurring. However, they provide a strong basis for temporal or cytological compartmentalization in RA disease natural history.

Current studies utilizing IHC analyses of synovial biopsies are insufficient to determine the distribution of the various pathotypes in RA patients but suggest that the diffuse myeloid and lympho-myeloid pathotypes are about equally frequent in RA patients with the fibroid pathotype being less common. There is growing evidence that patients with different RA pathotypes respond differently to various therapies, holding out the possibility that determining the RA pathotype of an individual patient's RA can direct the choice of the most effective therapy for that patient (i.e., personalized RA therapy) (Dennis 2014). This is an area of ongoing active investigation in RA therapy research (Pitzalis 2013, Donlin 2018, Mandelin 2018). However, already there is significant evidence indicating that patients with a myeloid-

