driven RA pathotype and/or with high densities of macrophages in their inflamed synovium respond best to anti-TNF α biologic therapy (Wijbrandts 2008, Dennis 2014), whereas patients with a fibroid pathotype do not respond significantly to anti-TNF α therapy. Although these results need to be confirmed and elaborated upon in further studies, they suggest that determination of the density of activated macrophages in the inflamed synovial membranes of patients with RA could facilitate identification of those RA patients who would most benefit from anti-TNF α therapy and/or those who would not receive benefit. Additional work in this field seeks to determine if similar associations between the efficacies of other treatments and synovial pathotypes can identify those treatments that are most effective in patients with lympho-myeloid and/or fibroid RA pathotypes. Such results, if attained, would provide a great benefit to RA patients by enabling personalized delivery of optimal treatments to all RA patients. The study to be conducted (NAV3-32) is designed to establish the correlation between Tc 99m tilmanocept localization to RA inflamed joints and the number and density of CD206 expressing cells (i.e., macrophages) in the inflamed joints as determined by IHC evaluations of synovial biopsy specimens. If this study is successful, Tc 99m tilmanocept imaging may be able to discriminate the fibroid pathotype from the myeloid and lymphoid pathotypes and may be able discriminate all 3 pathotypes from each other.

Previously generated results from clinical imaging studies conducted by Navidea and extensive peer reviewed scientific literature strongly indicate that Tc 99m tilmanocept can enable non-invasive imaging of aggregates of CD206-expressing cells associated with various pathologies using planar scintigraphy. While it has been suggested that synovial biopsy and IHC evaluations might be translatable to common rheumatological clinical practice, there are 5 reasons why quantitative assessment of CD206 positivity enabled by Tc 99m tilmanocept imaging may be preferred to synovial biopsies for evaluations of RA patients.

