#### 4.2.2 Secondary Efficacy Variables

Co-expression of the CD68, CD163, and CD206 markers will be analyzed by 2 methods. First, by providing the product-moment and Spearman rank correlation matrices of the IHC field measurements (that is, the fraction of macrophages expressing the markers will not be multiplied by the synovitis score). Descriptive statistics of the data triplets used to calculate the correlation matrices will be

provided (number of data triplets, means, standard deviations, minima, medians, and maxima). In the second method, histological sections will undergo immunofluorescent staining for the 3 markers and DAPI. For each section evaluated, up to 50 cells from the synovial sublining will be identified for each of the 3 markers. For each identified cell (up to 150/section), the rate of co-expression of the 3 markers will be determined. For sections with sparse marker expressing cells, four microscope fields will be randomly selected. Co-expression of the markers will be quantified for any cell observed expressing a marker.

The ability of  $TUV_{joint}$  to discriminate among lympho-myeloid, diffuse myeloid, and pauci-immune fibroid RA disease types will be evaluated with a multinomial logistic regression model. The model in terms of the logit (log odds) of the outcome is defined as:

$$\ln \frac{\pi_j}{1 - \pi_j} = \alpha_j + \beta_j X$$

where

$j$  = category of the outcome

$\frac{\pi_j}{1 - \pi_j}$  = odds

$\alpha$  = intercept

$\beta$  = slope

$X = TUV_{joint}$

RA type will be the response variable and  $TUV_{joint}$  will be the explanatory variable. ROC curves will be generated using the lympho-myeloid type as the base class. The marginal distribution of disease type will be summarized with a frequency table, while the marginal distribution of  $TUV_{joint}$  will be summarized with descriptive statistics (number of data pairs, mean, standard deviation, minimum, median and maximum). The joint distribution will be graphically summarized with box plots showing the conditional distribution of  $TUV_{joint}$  for each disease type.

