#### 4.2.3 Exploratory Efficacy Endpoints

Expression of CD3, CD20, CD55, CD68, CD163, CD206, and TE7 biomarkers and their association with  $TUV_{joint}$  will be assessed with the Pearson (product-moment) and the Spearman (rank) correlation matrices calculated for each measurement of expression (IHC, RNAseq, and [optional] flow cytometry). The marginal distributions will be summarized with descriptive statistics (number of complete data points, means, standard deviations, minima, medians, and maxima). The joint distribution will be presented graphically in a windowpane plot of the scatter diagrams.

Expression of CD206, CD163, and CD68 genes in mRNA will be measured with cDNA probes. The  $TUV_{joint}$  values concentrations will be regressed on the mRNA

abundance as determined by RNA-seq values. The marginal distributions will be summarized with descriptive statistics (number of complete data points, means, standard deviations, minima, medians, and maxima). The joint distribution will be presented with a windowpane plot of the scatter diagrams. The regression coefficients will be presented with the estimated residual covariance matrix.

The number, size, and co-expression of CD68, CD163, and CD206 expressing macrophages measured by flow cytometry and their relationship with  $TUV_{joint}$  will be assessed with the Pearson (product-moment) and Spearman (rank) correlation matrices. The marginal distributions of all variables will be summarized by descriptive statistics (number of complete data points, means, standard deviations, minima, medians, and maxima). The joint distributions will be presented graphically in a windowpane plot of the scatter diagrams.

The ability of  $TUV_{global}$  to discriminate among lympho-myeloid, diffuse myeloid, and pauci-immune fibroid RA disease types will be evaluated with a multinomial logistic regression model. The model in terms of the logit of the outcome is defined as:

$$\ln \frac{\pi_j}{1 - \pi_j} = \alpha_j + \beta_j X$$

where

j = category of the outcome

$\frac{\pi_j}{1 - \pi_j}$  = odds

$\alpha$  = intercept

$\beta$  = slope

X =  $TUV_{global}$

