RA type will be the response variable and  $TUV_{global}$  will be the explanatory variable. ROC curves will be generated using the lympho-myeloid type as the base class. The marginal distribution of disease type will be summarized with a frequency table, while the marginal distribution of  $TUV_{global}$  will be summarized with descriptive statistics (number of data pairs, mean, standard deviation, minimum, median and maximum). The joint distribution will be graphically summarized with box plots showing the conditional distribution of  $TUV_{global}$  for each disease type.

If it is found (based on the ROC curves from the multinomial logistic regressions) that  $TUV_{joint}$  and  $TUV_{global}$  can discriminate between the three RA disease types, then no additional analyses will be performed. However, if this is not the case, then two binary logistic regression analyses, with fibroid vs. non-fibroid disease type as the response and  $TUV_{joint}$  and  $TUV_{global}$  as predictors, respectively, will also be conducted.

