54	ECG Parameters Descriptive Statistics (Safety Population)	X	X
55	Summary of Treatment Emergent Adverse Events (Safety Population)	X	X
56	Number and Percent of Subjects with TEAEs (Safety Population)	X	X
57	Descriptive Statistics of $TUV_{joint}$ by Fibroid vs. Non-Fibroid Type (ITA Population)	X	X
58	Descriptive Statistics of $TUV_{joint}$ by Fibroid vs. Non-Fibroid Type (PP Population)	X	
59	Descriptive Statistics of $TUV_{global}$ by Fibroid vs. Non-Fibroid Type (ITA Population)	X	
60	Descriptive Statistics of $TUV_{global}$ by Fibroid vs. Non-Fibroid Type (PP Population)	X	

Figure No.	Figure Title	Included in Final Figures	Shown in Appendix B
Fig1	Scatterplot of the Joint Distribution of CD206 Macrophage Count and $TUV_{joint}$	X	X
Fig2	Boxplots of the Conditional Distribution of $TUV_{joint}$ for Each Category of Synovitis Score	X	X
Fig3	Boxplots of the Conditional Distribution of $TUV_{global}$ for Each Category of Synovitis Score	X	
Fig4	ROC Curves by RA Disease Type, Logistic Regression with $TUV_{joint}$	X	X
Fig5	ROC Curves by RA Disease Type, Logistic Regression with $TUV_{global}$	X	
Fig6	Conditional Distribution of $TUV_{joint}$ by RA Disease Type	X	X
Fig7	Joint Distribution of CD3, CD20, CD55, CD68, CD163, CD206, and TE7 Biomarkers Association with $TUV_{joint}$	X	X
Fig8	Joint Distribution of CD68, CD163, and CD206 in mRNA	X	X
Fig9	Joint Distribution of CD68, CD163, and CD206 Measured by Flow Cytometry	X	X

Data Listing No.	Data Listing Title	Included in Final Listings	Shown in Appendix B
DL1	Subject Disposition Data Listing	X	X
DL2	Inclusion/Exclusion Data Listing	X	X
DL3	Protocol Deviations Data Listing	X	X
DL4	Demographics Data Listing	X	X
DL5	Subjects Excluded from ITA Population Data Listing	X	X
DL6	Subjects Excluded from PP Population Data Listing	X	X
DL7	Subjects Excluded from Safety Population Data Listing	X	X
DL8	Medical History Data Listing	X	X
DL9	Prior and Concomitant Medications Data Listing	X	X
DL10	Prior and Concomitant RA Medications Data Listing	X	X
DL11	Adverse Events Data Listing	X	X
DL12	Occurrence of TEAEs Associated with Concomitant Medications or Class of Medications	X	X
DL13	Subject Laboratory Profiles – Hematology Data Listing	X	X
DL14	Subject Laboratory Profiles – Serum Chemistry Data Listing	X	
DL15	Subject Laboratory Profiles – Urinalysis Data Listing	X	
DL16	Subject Laboratory Profiles – Rheumatology Panel Data Listing	X	
DL17	Physical Exam Data Listing	X	X
DL18	ACR/EULAR 2010 Classification Data Listing	X	X

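### SAP 4.2.2 and 4.2.3 name a multinomial model but write one-versus-rest logits, and the ROC condition on the fibroid regressions has no criterion (minor)

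*SAP*

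**What the plan says.** SAP 4.2.2 has pathotype (lympho-myeloid, LM; diffuse myeloid, DM; pauci-immune fibroid) as a three-category response with TUV_joint as the single explanatory variable, and calls the model multinomial logistic. It continues: "The model in terms of the logit (log odds) of the outcome is defined as", followed by ln(π_j/(1−π_j)) = α_j + β_jX, with j described only as the outcome category. SAP 4.2.3 does the same for TUV_global: "The model in terms of the logit of the outcome is defined as", then the identical equation.

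A base class is named, but only for the curves: "ROC curves will be generated using the lympho-myeloid type as the base class". The protocol synopsis (plan for statistical analysis) links the curves to the model: "ROC curves will be generated for the multinomial logistic model using the lympho-myeloid type as the base class". It also rules out inferential statistics for these endpoints. The protocol prints no equation.

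The last paragraph of SAP 4.2.3 sets a condition based on the ROC curves. If TUV_joint and TUV_global "can discriminate between the three RA disease types, then no additional analyses will be performed". Otherwise two binary logistic regressions of fibroid versus non-fibroid type are fitted, one per TUV score.

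**The concern.** There are two separate defects.

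**The equation.** It gives every category its own odds against all the others. That is not the named model, and it leaves the LM base class with no role. A programmer who follows the formula fits something different from one who follows the name.

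**The condition.** The SAP does not say what counts as discriminating: no AUC cut-off, no interval rule, no statement of which curves count, and no rule for when one TUV score succeeds and the other does not. Because inference is excluded, no test can be read in as the implied criterion. The decision is therefore made by eye after the data are seen.

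The condition also fits the rationale in Protocol 1.1 poorly. That section says "High densities of macrophages can occur in both the myeloid and lymphoid pathotypes, whereas the fibroid pathotype is largely devoid of both macrophages" (lymphoid cells are the other type it names), so LM and DM may have similar uptake. It also says that imaging, if the study succeeds, "may be able to discriminate the fibroid pathotype from the myeloid and lymphoid pathotypes", a hoped-for result in its own right. A chance split between LM and DM could cancel the models that address that contrast directly.

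**Working it through.** The plan gives no figure to reproduce here. All TUV means, SDs, correlations and AUC cut-offs below are assumptions, because the documents give none.

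**1. The form of the model.** A baseline-category model for three types has 2 logits and 4 parameters. The printed form has 3 logits and 6 parameters, with no sum constraint. Its probabilities sum to 1 at every X only if all slopes are zero. As X → +∞, each logit with a positive slope contributes 1, each with a negative slope 0, and each with zero slope a constant strictly between 0 and 1. As X → −∞, positive and negative swap.
- With no zero slope, a total of 1 at both ends needs exactly one positive and one negative slope, but there are three slopes.
- With one or two zero slopes, the constants would have to bring a whole number to 1 at one end and a different number to 1 at the other, or be 0 or 1 themselves. Neither is possible.

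**2. Size of the failure.** Large-sample fit, assumed means LM 1, DM 0.5, fibroid −0.5, SD 1. The three intercepts are −1.131, −0.762 and −0.549.
- At X = 0: 1/(1+e^1.131) + 1/(1+e^0.762) + 1/(1+e^0.549) = 0.244 + 0.318 + 0.366 = 0.928.
- At X = 3: 0.813 + 0.449 + 0.015 = 1.277.

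With means LM 2, DM 1, fibroid 0, SD 1, the sums run from 0.85 to 1.33.

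**3. When the equation changes an AUC.** Let p = Φ(1/√2) = 0.760, with equal shares.
- Means 2, 1, 0, DM versus the rest: the one-versus-rest slope for DM is zero, so the AUC is 0.50. The multinomial DM probability peaks in the middle, giving p² + (1−p)² = 0.578 + 0.058 = 0.635.
- Means 1, 1, 0, DM versus the rest: (0.5 + 0.760)/2 = 0.63 under both forms.
- Pairwise curves that rank subjects by TUV are the same under both forms.

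So an AUC changes only if the formula is coded literally, class-versus-rest curves are drawn, and LM and DM uptake differ.

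**4. The condition.** Inputs:
- N = 24, the top of the range in SAP 1.3.
- Fibroid as the rarest type at 25% (prevalence illustrated in SAP 1.3; Protocol 1.1 calls fibroid less common and the other two about equally frequent). So 24 × 0.25 = 6 fibroid and (24 − 6)/2 = 9 each of LM and DM.
- Assumed means 1, 1, 0 and SD 1, so LM and DM truly do not differ and any pass is due to chance.
- The same means for both TUV scores, with within-type correlation 0 to 0.8.

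Share of simulated trials in which the condition passes and the fibroid models are switched off:

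| Curves that must pass | Scores required | AUC ≥ 0.60 | AUC ≥ 0.70 |
|---|---|---|---|
| DM v LM and fibroid v LM | both | 18–26% | 1–5% |
| DM v LM and fibroid v LM | a single score | 42% | 11% |
| All three pairs | both | 13–21% | 0.5–2.6% |
| All three pairs | a single score | 37% | 7% |

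The first row agrees with the second at zero correlation: 0.42² = 0.18 and 0.11² = 0.01. The single-score rows take one score judged alone.

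**5. What is lost when the condition passes.** In the all-pairs, single-score case at 0.60, the pooled fibroid versus non-fibroid AUC averages 0.80 when the condition passes and 0.74 when it fails.

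**The case against.** The strongest reply is that little is at stake. The name of the model and the base class both point to a baseline-category logit, which is probably what would be programmed, so the formula is a slip of notation. On the condition, the wording joins TUV_joint and TUV_global, so the plain reading needs both scores to succeed before anything is dropped, and that brings the chance figures down. Any rule that includes fibroid versus LM passes only when fibroid has already separated from LM, so the contrast is usually visible in the curves when the extra models are skipped. Tables 57 to 60, titled "by Fibroid vs. Non-Fibroid Type (ITA Population") and the per-protocol equivalents, are listed without any condition. The plot in the Figure 4 shell is not in the text available and may show which curves are meant.

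Most of this stands, and it sets the weight. Two things remain. The printed model is still not the named one, in two places. And neither a figure shell nor descriptive tables supply the missing criterion or the conditional regressions; the Table 57 shell holds summary statistics only.

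A reader might infer that the pathotype ROC results will be wrong, or that the study is likely to lose its fibroid result. The documents support neither. The first needs all three circumstances in step 3 together, and Protocol 1.1 is nearer the case of similar LM and DM uptake, where the equation changes no AUC. The second overlooks the joint wording, the curves themselves and the unconditional tables.

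**Conclusion.** The point holds as a minor one. The equation in SAP 4.2.2 and 4.2.3 does not define the model those sections name. That follows from the text and needs no assumption about TUV.

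The condition at the end of SAP 4.2.3 is a choice made after the data are seen, with no stated rule. On the wording closest to the documents (both scores, two curves against LM), it would drop the fibroid models by chance in about 18 to 26% of trials at a cut-off of 0.60 and 1 to 5% at 0.70. If a single score decides, the figures are about 42% and 11%. These rest on the assumed means, SD, correlation and 9/9/6 split. They show how far the outcome depends on the unstated rule and do not predict this trial. The endpoints are secondary and exploratory with no inference planned, and the primary correlation is untouched.

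**What to change.** - In both SAP 4.2.2 and 4.2.3, replace the equation with ln(π_j/π_LM) = α_j + β_jX for j = diffuse myeloid and pauci-immune fibroid, and state that lympho-myeloid is the reference category.
- State that the ROC curves are DM versus LM and fibroid versus LM from that model, reported descriptively. Align the shells for Figures 4 and 5 if they show something else.
- Delete the condition in the last paragraph of SAP 4.2.3 and run the two fibroid versus non-fibroid logistic regressions (TUV_joint and TUV_global) in all cases. A pre-stated AUC rule would also close the gap, but it would need a cut-off, a choice of curves and a rule for combining the two scores. Dropping the condition needs none of these.

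The cost is two formulas, a few sentences, two small models and output tables for them, since Tables 57 to 60 are descriptive only. No new data are needed.

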#### 4.2.3 Exploratory Efficacy Endpoints

Expression of CD3, CD20, CD55, CD68, CD163, CD206, and TE7 biomarkers and their association with  $TUV_{joint}$  will be assessed with the Pearson (product-moment) and the Spearman (rank) correlation matrices calculated for each measurement of expression (IHC, RNAseq, and [optional] flow cytometry). The marginal distributions will be summarized with descriptive statistics (number of complete data points, means, standard deviations, minima, medians, and maxima). The joint distribution will be presented graphically in a windowpane plot of the scatter diagrams.

Expression of CD206, CD163, and CD68 genes in mRNA will be measured with cDNA probes. The  $TUV_{joint}$  values concentrations will be regressed on the mRNA

abundance as determined by RNA-seq values. The marginal distributions will be summarized with descriptive statistics (number of complete data points, means, standard deviations, minima, medians, and maxima). The joint distribution will be presented with a windowpane plot of the scatter diagrams. The regression coefficients will be presented with the estimated residual covariance matrix.

The number, size, and co-expression of CD68, CD163, and CD206 expressing macrophages measured by flow cytometry and their relationship with  $TUV_{joint}$  will be assessed with the Pearson (product-moment) and Spearman (rank) correlation matrices. The marginal distributions of all variables will be summarized by descriptive statistics (number of complete data points, means, standard deviations, minima, medians, and maxima). The joint distributions will be presented graphically in a windowpane plot of the scatter diagrams.

The ability of  $TUV_{global}$  to discriminate among lympho-myeloid, diffuse myeloid, and pauci-immune fibroid RA disease types will be evaluated with a multinomial logistic regression model. The model in terms of the logit of the outcome is defined as:

$$\ln \frac{\pi_j}{1 - \pi_j} = \alpha_j + \beta_j X$$

where

j = category of the outcome

$\frac{\pi_j}{1 - \pi_j}$  = odds

$\alpha$  = intercept

$\beta$  = slope

X =  $TUV_{global}$

RA type will be the response variable and  $TUV_{global}$  will be the explanatory variable. ROC curves will be generated using the lympho-myeloid type as the base class. The marginal distribution of disease type will be summarized with a frequency table, while the marginal distribution of  $TUV_{global}$  will be summarized with descriptive statistics (number of data pairs, mean, standard deviation, minimum, median and maximum). The joint distribution will be graphically summarized with box plots showing the conditional distribution of  $TUV_{global}$  for each disease type.

If it is found (based on the ROC curves from the multinomial logistic regressions) that  $TUV_{joint}$  and  $TUV_{global}$  can discriminate between the three RA disease types, then no additional analyses will be performed. However, if this is not the case, then two binary logistic regression analyses, with fibroid vs. non-fibroid disease type as the response and  $TUV_{joint}$  and  $TUV_{global}$  as predictors, respectively, will also be conducted.

